7.3. Retests, Unscheduled Visits and Early Termination Data

In general, for by-visit summaries, data recorded at the nominal visit will be presented. Unscheduled measurements will not occur for this study.

Listings will include all scheduled, and early termination discontinuation data.

7.4. Windowing Conventions

Allowed time window for each visit will be performed as mentioned in "Schedule of Activities", section 1.3 of protocol.

Table C: Intervals Between Study Visits

Interval	Planned Visit Interval*	Allowed Interval Range
Visit 1 → Visit 2	7 days	7 – 12 days
Visit 1 → Visit 3	60 days	56 – 74 days
Visit 3 → Visit 4	28 days	28 – 44 days
Visit 1 → Visit 5 (visit 5 occurring before protocol amendment 2 [08JUN2023])	180 days	180 – 194 days
Visit 1 → Visit 5 (visit 5 occurring on or after protocol amendment 2 [08JUN2023])	180 days	166 – 194 days
Visit 5 → Visit 6	28 days	28 – 44 days
Visit 1 → Visit 7	360 days	346 – 374 days

^{• * =} Number of days between the visits

Document: \\quintiles.net\Enterprise\Apps\sasdata\SAS\\SAS\GlaxoSmithKline\HPV\213749

(HPV9)\Biostatistics\Documentation\SAP\GSK 213749(HPV9-AS04-

001)_WZA97329_SAP_Final_v3.0_02FEB2024.docx

Author: PPD Version Number: 3.0

Version Date: 02FEB2024

Template No.: CS_TP_BS016 Revision 7 Reference: CS_WI_BS005

Page 28 of 48

Table D: Window Convention

Assigned Study Day	Visit Label as per Protocol	Visit Assigned
Day 1	Visit 1	Visit 1
Day 7 (Day 1 + 7 to 12 days)	Visit 2	Visit 2
Day 60 (Day 1 + 56 to 74 days)	Visit 3	Visit 3
Day 88 (Day 1 + 84 to 118 days)	Visit 4	Visit 4
Day 180 (Day 1 + 180 to 194 days) (visit 5 occurring before protocol amendment 2 [08JUN2023])	Visit 5	Visit 5
Day 180 (Day 1 + 166 to 194 days) (visit 5 occurring on or after protocol amendment 2 [08JUN2023])	Visit 5	Visit 5
Day 208 (Day 1 + 208 to 238 days)	Visit 6	Visit 6
Day 360 (Day 1 + 346 to 374 days)	Visit 7	Visit 7

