Recording of all SAEs, including SAEs related to study intervention, to study participation, to a concurrent GSK medication/vaccine ⁴	•	•	•	•	•	•	•	
Recording of AEs/SAEs leading to withdrawal of a participant from the intervention/study	•	•	•	•	•	•	•	
Recording of pregnancies and pregnancy outcomes ⁵	•	•	•	•	•	•	•	
Recording of pIMDs	•	•	•	•	•	•	•	See Table 21
Study Conclusion							•	See Section 4.3

(the table footnote continues on the next page)

* 18-26 years of age for Step 1 participants.

Note: In Germany, only adult participants between and including 18 to 26 years of age are to be included in this clinical study

** For Step 1 participants only

AE = adverse event; D = day; eDiary = electronic diary; LAR = legally authorized representative; pIMD = potential immune-mediated disease; SAE = serious adverse event

- is used to indicate a study procedure that requires documentation in the individual electronic case report form (eCRF)
- o is used to indicate a study procedure that does not require documentation in the individual eCRF
- The preferred location for measuring the temperature is the axilla. Fever is defined as body temperature ≥37.5°C/99.5°F.
- Blood samples should be collected prior to vaccine administration.
- Only for 200 participants (50/group) at pre-selected sites.
- The collection and reporting period starts once the participants' informed consent (and assent, if applicable) is obtained.
- ⁵ Follow-up of pregnancy outcomes will be done beyond Month 12.

Table 2 Intervals Between Study Visits

Interval	Planned Visit Interval*	Allowed Interval Range
Visit 1→Visit 2**	7 days	7 – 12 days
Visit 1→Visit 3	60 days	56 – 74 days
Visit 3→Visit 4	28 days	28 – 44 days
Visit 1→Visit 5	180 days	166 – 194 days
Visit 5→Visit 6	28 days	28 – 44 days
Visit 1→Visit 7	360 days	346 – 374 days

^{*}Number of days between the visits.

^{**}Visit 2 is for Step 1 participants only.

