9.3. Populations for Analyses

Populations for analyses in this study are defined in Table 19.

Table 19 Study Analyses Sets

Analysis set	Description				
Enrolled set	Participants who received a study vaccine or had a blood draw before study vaccine administration or were randomized. Note as per Good Clinical Practice (GCP) enrolled participants should have completed the informed consent process and participants should be eligible before initiating any study procedure.				
Exposed set (ES)	All participants who received a study vaccine. Analysis per group is based on the study vaccine administered.				
	A safety analysis based on the ES will include all vaccinated participants. An immunogenicity analysis based on ES will include all vaccinated participants for whom immunogenicity data are available.				
Per Protocol set (PPS)	The per protocol set for analysis of immunogenicity will be defined by time point (to include all eligible participants' data up to the time of important protocol deviations).				
	The PPS will include all evaluable participants in the ES:				
	Meeting all eligibility criteria.				
	• For whom the administration route of the vaccine was as according to protocol.				
	For whom the study vaccine was administered as per protocol.				
	Who did not receive a concomitant medication/product leading to exclusion from a PP analysis, as described in the protocol.				
	Who did not present with a intercurrent medical condition leading to exclusion from a PP analysis, as described in the protocol.				

Analysis set	Description
	 Who complied with the vaccination schedule, as specified in Table 1. Who complied with the timings of the post-vaccination blood sampling for immune response evaluation, as specified in Table 1.
	 For whom post-vaccination immunogenicity results are available for at least one antigen at the corresponding time points.

For discontinuation of study intervention and participant discontinuation/withdrawal details, see Section 7.

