6.1. Process for Analysis Set Assignment

- Definitions for analysis sets are provided below.
- Prior to database lock, a transfer of raw data from the electronic Case Report Form (eCRF) will occur, and
 participants will be assigned to analysis sets in accordance with the definitions in this SAP and the available
 data at that time. However, the protocol deviations will be monitored continuously throughout the study.
- Listings presenting participants excluded from each preliminary analysis set and reasons for exclusion will be
 prepared for sponsor review ahead of database lock in order to allow appropriate related data queries to be
 issued.
- Listings presenting participants excluded from each final analysis set and reasons for exclusion will be prepared
 for sponsor review ahead of unblinding for a final review and approval. However, for deviations that can only
 be assessed after unblinding such as vaccination errors these will be reviewed after unblinding.
- A Data Review meeting will be held to confirm analysis set assignment for each participant and any changes
 will be recorded. Changes will be implemented, and an updated analysis set assignment will be approved by the
 sponsor.

Document: \\quintiles.net\Enterprise\Apps\sasdata\SASb\SAS\GlaxoSmithKline\HPV\213749

(HPV9)\Biostatistics\Documentation\SAP\GSK_213749(HPV9-AS04-

001)_WZA97329_SAP_Final_v3.0_02FEB2024.docx

Author: PPD Version Number: 3.0

Version Date: 02FEB2024

Template No.: CS_TP_BS016 Revision 7 Reference: CS_WI_BS005

Page 25 of 48

- Sponsor authorization of the analysis sets will be necessary to unblind the data after the final database lock.
 Once approved, the study will be unblinded, analysis sets will be finalized including additional eliminations requiring unblinding, and the database will be locked.
- After database lock, the final analysis sets will be derived using the final study data, i.e., clinical database (eCRF), external vendor data (immunogenicity results), protocol deviations log and blinded data report.

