6.4. Per Protocol Set [PPS]

A per-protocol set (PPS) will be defined for all participants in the ES at each visit that meet the following criteria:

- Meeting all eligibility criteria
- For whom the administration route of the vaccine was as according to protocol
- For whom the study vaccine was administered per protocol
- Who did not receive a concomitant medication/product/vaccine leading to exclusion from a PP analysis, as
 described in the protocol
- Who did not present with an intercurrent medical condition leading to exclusion from a PP analysis, as described in the protocol
- Who complied with the vaccination schedule
- Who complied with the timings of the post-vaccination blood sampling for immune response evaluation
- For whom post-vaccination immunogenicity results are available for at least one antigen at the corresponding time points

The eliminations for the PPS will be adapted as per the timepoint analysis, e.g., for month 3 analysis only violations up to month 3 will be excluded.

Document: \\quintiles.net\Enterprise\Apps\sasdata\SAS\\SAS\GlaxoSmithKline\HPV\213749

(HPV9)\Biostatistics\Documentation\SAP\GSK_213749(HPV9-AS04-

001)_WZA97329_SAP_Final_v3.0_02FEB2024.docx

Author: PPD Version Number: 3.0

Version Date: 02FEB2024

Template No.: CS_TP_BS016 Revision 7 Reference: CS_WI_BS005

Page 26 of 48

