10.2. Protocol Deviations

During the study, Protocol Deviations (PDs) will be collected in a PD log, as detailed in the Protocol Deviations Management Plan (PDMP). All PDs will be assessed as either important or non-important. PDs will be reviewed by the sponsor, and their status confirmed by the time that all data are cleaned for the Final Analysis. A summary table presenting the number and percentage of participants with important PDs (i.e, those PDs associated to elimination from PPS) will be presented for participants in the ES. A listing of all PDs including an indicator of those excluded from the PPS and an indicator of COVID-19 causality will be provided.

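### The lower limit of the Visit 6 range in SAP Table D (Day 1 + 208) still rests on the superseded Visit 5 minimum of 180 days and conflicts with the 28 to 44 day interval

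*SAP*

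**What the plan says.** Protocol section 1.3, Table 2, allows Visit 5 at 166 to 194 days after Visit 1. Its "Visit 5→Visit 6" row allows 28 to 44 days between those two visits. SAP section 7.4 opens by deferring to that section: "Allowed time window for each visit will be performed as mentioned in" the protocol's schedule of activities. SAP Table C repeats the 28 to 44 day interval and splits the Visit 5 row by date: 180 to 194 days before 8 June 2023, and 166 to 194 days from then on.

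Table D, in the same section, restates the visits as days from Day 1. It also splits Visit 5, with the later row reading "Day 180 (Day 1 + 166 to 194 days) (visit 5 occurring on or after protocol amendment 2 [08JUN2023". Visit 6 has a single row with no split: "Day 208 (Day 1 + 208 to 238 days".

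On Per Protocol membership, SAP 6.4 requires participants "Who complied with the timings of the post-vaccination blood sampling for immune response evaluation" and names no table. Protocol Table 19 has the same criterion but refers to Table 1, which lists procedures by visit and holds no day ranges; those are in Table 2. For the primary Month 7 IgG estimand, SAP Table A excludes a participant whose blood sample is out of window, without saying which window.

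**The concern.** Two tables in one SAP section give ranges for Visit 6 that cannot both be met by some participants who follow the protocol. The Visit 5 rows were revised after the amendment, and the row that depends on them was not.

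Visit 6 is the Month 7 sample. It supplies the primary immunogenicity endpoint, the IgG geometric mean concentrations, analysed on the Per Protocol Set. It also supplies the exploratory between-group ratios meant to inform formulation selection for phase 3. SAP 16.1.3 repeats the primary analysis on the Exposed Set if more than 5% of participants are excluded. SAP 16.2.4 runs the exploratory ratios on the Per Protocol Set only. If a programmer took Table D as the test of being in window, participants who complied with the protocol would be lost from both analyses, and only the first has a fallback.

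**Working it through.** **Inputs.** Visit 3 range 56 to 74 days; Visit 5 range 180 to 194 days (before 8 June 2023) or 166 to 194 days (from that date); follow-on interval 28 to 44 days for Visit 3 to Visit 4 and for Visit 5 to Visit 6. All are in SAP Table C; protocol Table 2 agrees and carries the current Visit 5 range.

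**How Table D is built.** A dependent visit runs from (earliest prior visit + 28) to (latest prior visit + 44).

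- Visit 4: 56 + 28 = 84 and 74 + 44 = 118. Table D prints 84 to 118, an exact match.
- Visit 6, old Visit 5 range: 180 + 28 = 208 and 194 + 44 = 238. Table D prints 208 to 238, an exact match.
- Visit 6, current Visit 5 range: 166 + 28 = 194 and 194 + 44 = 238. Table D's lower limit does not match; its upper limit does.

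So only the lower limit is stale, by 208 − 194 = 14 days. The planned day of 208 (180 + 28) is still right as a planned day.

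**Where the tables conflict.** For Visit 5 on day d, the interval allows Visit 6 on d + 28 to d + 44, which is 17 days. Table D rejects those before 208.

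| Visit 5 day | Visit 6 allowed by interval | Rejected by Table D | Smallest gap Table D accepts |
|---|---|---|---|
| 166 | 194 to 210 | 14 of 17 | 42 |
| 173 | 201 to 217 | 7 of 17 | 35 |
| 179 | 207 to 223 | 1 of 17 | 29 |
| 180 | 208 to 224 | 0 of 17 | 28 |

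At the planned 28-day gap, every Visit 5 on days 166 to 179 gives a Visit 6 on days 194 to 207, outside Table D. From day 180 onward there is no conflict. These are calendar possibilities. They say nothing about how many participants fall there.

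**Can any absolute range do the job?** With Visit 5 up to day 194 and Visit 6 from day 208, Table D accepts a gap as short as 208 − 194 = 14 days. The longest is 238 − 180 = 58 days under the old Visit 5 range and 238 − 166 = 72 under the current one. With the lower limit corrected to 194, the accepted gaps run from 194 − 194 = 0 to 72 days, and day 194 lies in both the Visit 5 and the Visit 6 ranges. A range counted from Day 1 therefore cannot enforce 28 to 44 days.

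**Label check.** Two rows in Table C and two in Table D attach 8 June 2023 to amendment 2. SAP section 2 gives that date to amendment 3, and protocol Appendix 6 dates amendment 2 to 23 September 2022.

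**The case against.** The strongest reply is that Table D does not decide Per Protocol membership. Its columns give an assigned study day, a protocol visit label and an assigned visit, so it reads as a visit-labelling map, and SAP 7.3 presents by-visit data by nominal visit anyway. Section 7.4 defers to protocol section 1.3. SAP 10.2.1 defines a deviation as non-compliance with the protocol, GCP or the deviation guidelines, and a Visit 6 within 28 to 44 days breaches no protocol interval. SAP 10.2 describes important deviations as "those PDs associated to elimination from PPS", SAP 6.1 derives the final sets partly from the deviations log, and exclusions are reviewed before unblinding. A separate deviations management plan, not among the documents, may state the sampling rule explicitly.

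Most of this stands. It makes the protocol interval the probable rule and the harm conditional. It does not remove the contradiction: Table D is headed as the window convention, sits in the operative windowing section, and is not marked as excluded from timing checks. SAP 6.1 also says that "participants will be assigned to analysis sets in accordance with the definitions in this SAP", and section 6.4 names no table. Reviewers of the exclusion listings can catch a wrong exclusion only if they know which table applies.

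A reader might infer more than the documents support. They do not show that compliant participants will be dropped, because the text leans towards the interval. They do not show that the timing rule is undefined: the interval stands in Table C and protocol Table 2, and the silence of section 6.4 is only missing detail. Nor do they suggest bias between groups. The trigger would be visit timing in a randomised, observer-blind trial, and no reason is given for it to differ by group.

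**Conclusion.** The lower limit of the Visit 6 row in Table D is wrong as written for Visit 5 on or after 8 June 2023. It is 14 days too late by the table's own construction, and it conflicts with Table C and protocol Table 2 for Visit 5 on days 166 to 179. Nothing else in that row is wrong.

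The consequence depends on Table D being used to judge whether a sample is out of window, which the SAP's other text points away from. If it were so used, the likely cost is lost precision at Month 7: the primary objective is descriptive and the non-inferiority analyses are exploratory. The number affected cannot be derived from the documents. Severity: minor. The arithmetic is certain; the impact is unknown.

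**What to change.** Reconcile Table D with Table C and protocol Table 2 in three edits.

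1. Split the Visit 6 row by the date of Visit 5, as was done for the Visit 5 row: Day 1 + 208 to 238 for Visit 5 before 8 June 2023, and Day 1 + 194 to 238 for Visit 5 on or after it. The split should follow the Visit 5 date, since that determines which minimum applied.
2. Add one sentence to section 7.4 saying that Per Protocol timing is judged by the actual interval in Table C and protocol Table 2 (for Visit 6, days since Visit 5), and that Table D is not used for this. The row edit alone is not enough, because the corrected range admits gaps of 0 to 72 days and overlaps Visit 5 on day 194. The same sentence covers Visit 4, whose row needs no change.
3. Change the amendment number from 2 to 3 in the four rows that carry 8 June 2023.

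The cost is one split row, one sentence and four label corrections. No new data are needed, and there is almost no programming.

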7.5. Statistical Tests

The default significant level will be 5%; CIs will be 95% and all tests will be two-sided, unless otherwise specified in the description of the analyses.

7.6. Common Calculations

Geometric Mean Concentration/Titer (GMC/GMT):

Distributions of antibodies are generally skewed to the right (Nauta, 2010). Therefore, prior to any statistical analysis that assumes normally distributed observations, antibody concentrations or titers will be log10-transformed. GMC/GMTs and their 95% CI are computed by exponentiating (base 10) the least squares mean and 95% CI of the log10 titers.

Document: \\quintiles.net\Enterprise\Apps\sasdata\SASb\SAS\GlaxoSmithKline\HPV\213749

(HPV9)\Biostatistics\Documentation\SAP\GSK 213749(HPV9-AS04-

001)_WZA97329_SAP_Final_v3.0_02FEB2024.docx

Author: PPD Version Number: 3.0

Version Date: 02FEB2024

Template No.: CS_TP_BS016 Revision 7 Reference: CS_WI_BS005

Page 29 of 48

The GMC/GMT will be calculated using the following formula:

$$10^{\left(\frac{\sum_{i=1}^{n}\log 10(t_i)}{n}\right)}$$

Where $t_1, t_2, ..., t_n$ are n observed immunogenicity concentrations/titer.

Concentration below assay cut-off (i.e., <lower limit of quantification or < LLOQ) will be replaced by half the assay cut-off (LLOQ/2) for the purpose of GMC computation. Any concentrations above the upper limit of quantification (or ULOQ) will be set to the ULOQ value. No imputation for ULOQ will be performed for the sensitivity analysis of GMC/GMT and for the correlations and Deming's regression.

Seroconversion:

Defined as the appearance of antibodies (i.e., concentrations/titers greater than or equal to the cut-off value) in the serum of participants seronegative before vaccination.

For quantitative measurements, change from baseline will be calculated as:

• Test Value at Visit X – Baseline Value

7.7. Software Version

All analyses will be conducted using SAS version 9.4 or higher.

8. STATISTICAL CONSIDERATIONS

8.1. Adjustments for Covariates and Factors to be Included in Analyses

For details on the factors to be used in the analysis refer to section 17.1 and 17.2. The model will include all groups and country as fixed categorical effects in the ANOVA model.

Document: \\quintiles.net\Enterprise\Apps\sasdata\SAS\\SAS\GlaxoSmithKline\HPV\213749

(HPV9)\Biostatistics\Documentation\SAP\GSK_213749(HPV9-AS04-

001)_WZA97329_SAP_Final_v3.0_02FEB2024.docx

Author: PPD Version Number: 3.0

Version Date: 02FEB2024

Template No.: CS_TP_BS016 Revision 7 Reference: CS_WI_BS005

Page 30 of 48

8.2. Multicenter Studies

This study will be conducted by multiple investigators at multiple centers. The participants will be randomized to one of the 4 groups (refer to Table B in section 4.1) which will be performed in a 1:1:1:1 ratio prior to intervention to provide approximately 270 enrolled participants per group.

8.3. Missing Data

Missing data (missing, incomplete, or partial dates, AE measurement (including missing AE severity and relationship), prior and concomitant medications and death date) will be handled as per APPENDIX 2 of this analysis plan.

Missing immunogenicity data will not be imputed.

8.4. Examination of Subgroups

No subgroup analyses will be performed for this study.

9. OUTPUT PRESENTATIONS

APPENDIX 1 shows conventions for presentation of data in outputs.

The templates provided with this SAP describe the presentations for this study and therefore the format and content of the summary tables, figures, and listings to be provided by IQVIA Biostatistics. Statistical output numbering will follow 'ICH E3 Structure and Content of Clinical Study Reports'.

10. DISPOSITION AND WITHDRAWALS

All participants who are enrolled in the study (those who received a study intervention or were randomized) will be accounted for in this study.

Document: \quintiles.net\Enterprise\Apps\sasdata\SAS\SAS\GlaxoSmithKline\HPV\213749

(HPV9)\Biostatistics\Documentation\SAP\GSK_213749(HPV9-AS04-

001)_WZA97329_SAP_Final_v3.0_02FEB2024.docx

Author: PPD Version Number: 3.0

Version Date: 02FEB2024

Template No.: CS_TP_BS016 Revision 7 Reference: CS_WI_BS005

Page 31 of 48

10.1. Disposition

Participant disposition, withdrawals, and reasons for exclusion from each analysis set, including inclusion as well as exclusion criteria will be presented for the ENR. Specifically, the number of participants, vaccinated, completed the study, discontinuing the study and the reason for discontinuation will be summarized by study group for the ENR. Additionally, the number of participants returning for each visit for the ES will be presented. The number of participants enrolled by age category (preterm newborn – gestational age < 37 weeks, newborn (0-27 days), infant and toddler (28 days to 23 months), children (2-11 years), adolescents (12-17 years), 18-64 years, 65-84 years and >=85 years) will be summarized by study group.

A listing of the disposition for all participants with early withdrawal or discontinuation due to having Coronavirus Disease 2019 (COVID-19) or COVID-19 related issues information will be provided. The number of participants who discontinue the study due to COVID-19 will also be summarized by study group.

10.2. Protocol Deviations

During the study, Protocol Deviations (PDs) will be collected in a PD log, as detailed in the Protocol Deviations Management Plan (PDMP). All PDs will be assessed as either important or non-important. PDs will be reviewed by the sponsor, and their status confirmed by the time that all data are cleaned for the Final Analysis. A summary table presenting the number and percentage of participants with important PDs (i.e, those PDs associated to elimination from PPS) will be presented for participants in the ES. A listing of all PDs including an indicator of those excluded from the PPS and an indicator of COVID-19 causality will be provided.

10.2.1. Protocol Deviations Related to Study Conduct

A PD is any non-compliance with the clinical trial protocol, GCP, or protocol deviation guidelines requirements. The non-compliance may be either on the part of the participant, the site investigator, the study site staff or the sponsor.

